4.4. Safety Objectives

The following safety objectives are as follows:

- To compare QW tirzepatide 5 mg, 10 mg, and 15 mg to placebo through the end of the safety follow-up period for
 - treatment-emergent adverse events (TEAEs)
 - early discontinuation of study drug due to adverse events (AEs)
 - adjudicated pancreatic AEs
 - serum calcitonin
 - incidence of allergic and hypersensitivity reactions
 - incidence of treatment-emergent antidrug antibodies to tirzepatide
 - mean change in systolic and diastolic blood pressure and heart rate from baseline
 - occurrence of hypoglycemic episodes, and
 - incidence of initiation of rescue therapy for severe, persistent hyperglycemia.

4.5. Pharmacokinetics

[figure not shown]
To characterize the pharmacokinetics (PK) of QW tirzepatide 5 mg, 10 mg, and 15 mg doses and evaluate the relationship between tirzepatide exposure and safety, tolerability, and efficacy measures for population PK and PD parameters.

5. Study Design

5.1. Summary of Study Design

Study I8F-MC-GPGI (GPGI) is a multicenter, randomized, double-blind, parallel, multinational, placebo-controlled Phase 3 study which will assess the safety and efficacy of the addition of 5 mg, 10 mg, or 15 mg tirzepatide, or placebo for change from baseline in HbA1c in patients with type 2 diabetes mellitus (T2DM) receiving titrated basal insulin glargine (with or without metformin) over 40 weeks of treatment.

Figure GPGI.5.1 illustrates the study design.

Abbreviation: QW = once weekly.

^a Stabilization Period = first 4 weeks after randomization, with restricted insulin dose adjustments. Insulin Glargine Titration Period Weeks 4 to 40 (end of treatment/end of study), with unrestricted insulin dose adjustments. Maintenance Period = Weeks 24 to 40 (end of treatment/end of study), the period when insulin glargine dose is expected to be stable.

Figure GPGI.5.1. Illustration of study design for Clinical Protocol I8F-MC-GPGI.

Study Period I (Screening and Lead-in)

Screening (Visit 1)

The purpose of screening procedures at Visit 1 is to establish initial eligibility and to obtain blood samples for laboratory assessments needed to confirm eligibility at Visit 2. Patients who

meet all applicable inclusion criteria and none of the applicable exclusion criteria at Visit 1 will continue on their prestudy therapy until Visit 2.

Lead-in (Visit 2 to Visit 3)

At Visit 2, the screening laboratory results will be reviewed, and patient eligibility will be established with the exception of retinopathy status. A dilated fundoscopic exam will be performed between Visit 2 and Visit 3 as results are required to confirm eligibility.

Study Period II (40-week treatment period)

Randomization (Visit 3)

At Visit 3, patients will perform all required baseline study procedures (including the collection of all baseline laboratory measures) prior to randomization and prior to taking the first dose of study drug.

Treatment Period: General Considerations

The treatment period will last 40 weeks, starting with a 4-week stabilization period immediately after randomization and followed by a 36-week glargine titration period. The maintenance period is defined as a part of the titration period when the insulin glargine dose is expected to be stable and optimized (Weeks 24 to 40).

The starting dose of tirzepatide will be 2.5 mg QW for 4 weeks, followed by an increase to 5 mg QW, for the duration of the study in the 5 mg group. For the 10 mg group, the starting dose of tirzepatide will be 2.5 mg QW for 4 weeks, then the dose will be increased by 2.5 mg every 4 weeks (2.5 to 5 to 7.5 to 10 mg) until the 10 mg dose is reached and maintained for the duration of the study. For the 15 mg group, the starting dose of tirzepatide will be 2.5 mg QW for 4 weeks, then the dose will be increased by 2.5 mg every 4 weeks (2.5 to 5 to 7.5 to 10 to 12.5 to 15 mg) until the 15 mg dose is reached and maintained for the duration of the study. For the placebo group, patients will inject matched QW placebo for the duration of the study.

Postrandomization period (end of Visit 3 to Visit 14)

Stabilization Period (End of Visit 3 through Visit 7)

The main purposes of this period are to introduce randomized study drugs (QW tirzepatide or QW placebo) in a safe manner and to assure regular and correct use of the self-monitoring and insulin dose adjustment procedures and study diaries during the entire study. In an effort to allow appropriate time for tirzepatide to reach steady state, insulin glargine dose adjustments during the 4-week stabilization period should be restricted to those needed in case of significant safety risks due to inadequate insulin dose (hypoglycemia or severe hyperglycemia) in which case patients should be instructed to contact the sites to adjust the insulin glargine dose per the treat-to-target (TTT) algorithm. In addition, for patients with baseline HbA1c $\leq 8.0\%$, the insulin glargine dose will be decreased by 20% immediately after randomization, no later than 7 days after the first dose of study drug and will then remain unchanged during the stabilization period to decrease the

risk of hypoglycemia. The insulin glargine dose will remain unchanged if baseline HbA1c is >8.0%.

Titration Period (End of Visit 7 through Visit 22)

At the beginning of the titration period, the patients will be instructed to start using the TTT algorithm without restrictions in order to reach the optimal dose of insulin glargine as soon as possible. The patients will be requested to perform an insulin dose assessment once weekly during this period.

Study Period III (Safety Follow-up Period)

Safety follow-up (Visit 801) visits

All patients who complete the treatment period are required to complete Visit 801, a safety follow-up visit, approximately 4 weeks after their last visit. Patients discontinuing the study early and performing an early termination (ET) visit will also be asked to perform the safety follow-up visit, so that the safety follow-up visit will be their last visit. During the safety follow-up period, patients will not receive study drug. Initiation of new antihyperglycemic therapy for the safety follow-up period will not be classified as “rescue therapy.”

5.2. Sample Size Determination

The trial is powered to assess superiority of tirzepatide 10 mg and 15 mg relative to the primary endpoint (mean change in HbA1c from baseline to 40 weeks).

The power is assessed based on the following assumptions:

- each of the 10- and 15-mg tirzepatide treatment groups will be tested in parallel against placebo at a 2-sided 0.025 significance level
- use of a 2-sample t-test utilizing HbA1c data collected before initiation of any rescue medication or premature treatment discontinuation with no more than 28% of subjects initiating rescue medication or prematurely discontinuing treatment in each treatment group
- 0.6% greater mean reduction in HbA1c from baseline for 10 and 15 mg tirzepatide compared with placebo
- 1:1:1:1 randomization, and
- a common standard deviation (SD) of 1.1%.

On the basis of these assumptions, a sample size of 472 subjects is required to ensure at least 90% power to demonstrate that tirzepatide 10 mg and/or 15 mg are superior to placebo relative to the primary endpoint. Furthermore, this sample size will ensure 90% power for the superiority evaluation conducted using an analysis of covariance (ANCOVA) utilizing all available HbA1c data at 40 weeks with missing data imputed with a conservative multiple imputation method (as described in Section 6.12.1.3), provided a 0.6% greater mean reduction in HbA1c from baseline for 10 and 15 mg tirzepatide compared with placebo and SD increases to no more than 1.3% due

to the inclusion of data on rescue medications and after premature treatment discontinuation and imputation of missing data.

5.3. Method of Assignment to Treatment

Approximately 472 patients who meet all criteria for enrollment will be randomized to one of the study treatment arms at Visit 3. Assignment to treatment arms will be determined by a computer-generated random sequence using an interactive web response system (IWRS). Patients will be randomized in a 1:1:1:1 ratio to receive 5 mg tirzepatide, 10 mg tirzepatide, 15 mg tirzepatide, or placebo. The randomization will be stratified by country, baseline HbA1c concentration ($\leq 8.0\%$, $>8.0\%$ [≤ 64 , >64 mmol/mol]), and baseline metformin use (Yes/No).

6. A Priori Statistical Methods

6.1. Populations for Analyses

For purposes of analysis, [Table GPGI.6.1](#) defines analysis populations/data sets.

Table GPGI.6.1. Analysis Populations/Data Sets

Population/Data Set	Description
Screened population	All participants who sign informed consent
Randomized population	All patients who are randomly assigned a treatment arm
Modified intention-to-treat (mITT) population	All randomly assigned participants who are exposed to at least 1 dose of study drug. In the event of a treatment error, participants will be analyzed according to the treatment they were randomized.
Efficacy analysis set (EAS)	Data obtained during Study Period II from the mITT population, excluding patients discontinuing study drug due to inadvertent enrollment and data after initiating rescue antihyperglycemic medication or early discontinuation of study drug (last dose date + 7 days).
Full analysis set (FAS)	All available data obtained during Study Period II from the mITT population, regardless of adherence to study drug or initiation of rescue antihyperglycemic medication. Patients who discontinued study drug due to inadvertent enrollment will be excluded.
Safety analysis set (SS)	All available data obtained during Study Periods II and III from the mITT population, regardless of adherence to study drug or initiation of new antihyperglycemic medication.

6.2. General Considerations

Statistical analysis of this study will be the responsibility of Eli Lilly and Company (Lilly) or its designee. All statistical analyses will be conducted with SAS Version 9.4 or higher unless otherwise stated. Any change to the data analysis methods described in the protocol will require an amendment only if it changes a principal feature of the protocol. Any other changes to the data analysis methods described in the protocol, and the justification for making the change, will be described in the SAP or the clinical study report (CSR). Some analyses and summaries described in this analysis plan may not be conducted if not warranted by data (e.g., few events to justify conducting an analysis). Listings of events will be provided in such situations. Additional analyses of the data may be conducted as deemed appropriate without further changes made to the protocol or SAP, even after the primary or final database locks (DBL).

Additionally, to avoid potential selection biases, unless stated otherwise, statistical summaries and analyses will be conducted based on randomized maintenance dose regardless of the actual treatment received by the patient.

Unless specified otherwise, the last measurement during Visit 1 to Visit 3 (including unscheduled visits) collected prior to or on the first dose day will serve as baseline.

- For immunogenicity, data collected up to the first dose time will serve as baseline.
- For lab and ECG, baseline needs to be prior to or within one hour after the first dose time.
- For patient-reported outcomes, data collected at Visit 3, regardless of the timing relative to first dose, will serve as baseline.

There will be 2 estimands of interest in evaluating the primary and secondary efficacy objectives. The first estimand, the “efficacy” estimand, represents efficacy prior to discontinuation of study drug without the confounding effects of rescue therapy for severe persistent hyperglycemia. Analyses relative to the “efficacy” estimand will be conducted using the efficacy analysis set (EAS). The second estimand, the “treatment-regimen” estimand, represents the efficacy irrespective of adherence to investigational product or introduction of rescue therapy for severe persistent hyperglycemia. Analyses relative to the “treatment-regimen” estimand will be conducted using the full analysis set (FAS).

Unless specified otherwise, safety analyses will be conducted relative to the “treatment-regimen” estimand using the safety analysis set (SS).

The end of study participation for a patient will be the earliest of date of death, date of withdrawal from further participation in the study, or date of the safety follow-up visit (Visit 801). For patients considered to be lost to follow-up, end of study participation will be the date of lost to follow-up reported by the investigator. Patient data included in the database after the last date of study participation (date of death, date of early termination or date of safety follow-up) will be excluded from statistical analyses. A listing of such data may be provided.

Summary statistics for categorical measures (including categorized continuous measures) will include sample size, frequency, and percentages. Summary statistics for continuous measures will include sample size, mean, SD, median, minimum, and maximum. The summary statistics will be presented by nominal visit.

Statistical treatment comparisons will only be performed between tirzepatide doses and placebo. Comparisons among tirzepatide arms will not be performed unless specified otherwise.

Statistical summaries and results of statistical analyses will be displayed in the following treatment order: 5 mg tirzepatide, 10 mg tirzepatide, 15 mg tirzepatide, placebo.

6.3. Adjustments for Covariates

The study is stratified by country, HbA1c ($\leq 8.0\%$, $> 8.0\%$ [≤ 64 , > 64 mmol/mol]) at screening, and baseline metformin use (Yes/No). Where necessary to be included as a fixed effect in statistical models, countries with fewer than 10 randomized patients will be pooled into one category (pooled country). For HbA1c related analyses, country/pooled country and baseline metformin use (Yes/No) will be used as fixed effects and baseline HbA1c as a covariate. For

other efficacy analyses, country/pooled country, baseline HbA1c ($\leq 8.0\%$, $>8.0\%$ [≤ 64 , >64 mmol/mol]), and baseline metformin use (Yes/No) will be used as fixed effects and respective baseline value as a covariate. Fixed effects will be based on the information collected in the clinical database.

6.4. Handling of Dropouts or Missing Data

For the primary and secondary efficacy endpoint analyses subject to type 1 error rate control, data for patients with missing values at the 40-week visit will be imputed based on the method described in Section 6.12.1.3. Unless specified otherwise, imputation of missing data will be limited to primary and key secondary efficacy endpoint analyses. Any other secondary or exploratory efficacy parameter values or safety laboratory values that are missing will not be explicitly imputed.

6.5. Multicenter Studies

To investigate potential regional influences on efficacy, country/pooled country will be used as a fixed effect in the primary and secondary efficacy analyses.

6.6. Multiple Comparisons/Multiplicity

The type 1 error rate control strategy for the primary and key secondary efficacy objectives is illustrated in Section 6.12.3. No multiplicity adjustments will be made for conducting separate analyses relative to the “efficacy” and “treatment-regimen” estimands, evaluating other secondary or exploratory efficacy objectives, or safety assessments.

6.7. Patient Disposition

Reasons for screen failures as reported by investigators will be summarized.

A listing of final study disposition and a listing of randomized treatment assignment (planned treatment) for all randomized patients will be provided. Final study disposition and the study treatment disposition for all randomized patients will be summarized by planned study treatment.

6.8. Patient Characteristics

A listing of patient demographics will be provided for all randomized patients. All demographic and baseline clinical characteristics will be summarized by study treatment for all randomized patients. Baseline demographic and clinical characteristics of special interest include

- age
- gender
- race
- ethnicity
- weight
- country of enrollment

- HbA1c
- fasting serum glucose
- insulin glargine daily dose, and
- duration of T2DM.

6.9. Prior and Concomitant Therapy

Summary of prior glucagon-like peptide-1 receptor agonist (GLP-1 RA) use by type and treatment arm will be provided.

Prespecified concomitant medications of interest ongoing at randomization will be summarized by treatment. Additionally, medications of interest initiated after randomization and changes to medications of interest used at randomization will be summarized. Concomitant therapies will be mapped using the World Health Organization (WHO) DRUG dictionary in the clinical trial database and will be further classified using Anatomic-Therapeutic-Chemical (ATC) codes for reporting purposes.

Concomitant medication summaries of interest include

- baseline antihypertensive therapy, by type
- baseline lipid lowering therapy, by type
- baseline antihyperglycemic therapy
- utilization of new antihyperglycemic therapy during Study Period II, and also during combined Study Periods II and III
- changes to baseline medication in Period II:
 - antihypertensive therapy
 - lipid lowering therapy
 - antihyperglycemic therapy
- changes to baseline medication during combined Study Periods II and III:
 - antihyperglycemic therapy
- rescue therapy and
- initiation of following medication in Study Period II:
 - antidiarrheal medication
 - antiemetic medication.

6.10. Treatment Exposure and Compliance

A listing of patients randomized but not receiving study treatment will be provided, if applicable. The listing will include patient identification, randomized treatment arm, and the reason for not receiving study treatment (if the data is available).

A summary of duration to follow-up (defined as time in days from date of randomization to date of safety follow-up, date of early study discontinuation or date of death) and duration on study treatment (defined as time in days from date of first dose of study treatment to date of last dose of study treatment plus 7 days) will be provided by study treatment.

6.10.1. Exposure and Compliance

The number of patients prematurely discontinuing study treatment prior to the 40-week visit will be provided by study treatment. Reasons for prematurely discontinuing study treatment prior to the 40-week visit will be provided by study treatment. Time-to-event analysis of premature study treatment discontinuation will be conducted.

A listing of patients who re-initiate tirzepatide/placebo due to missing ≥ 3 consecutive doses may be produced if data warrants.

Summary information on total daily dose of insulin glargine will be reported by visit. Information related to insulin glargine in regard to compliance to treat-to-target algorithm including number of assessments performed correctly, number of assessments that required a dose change, number of assessments for which the outcomes were correctly followed by the patient, and reasons for noncompliance will be summarized.

Overall treatment compliance will be defined as taking at least 75% of the scheduled study drug or insulin glargine injections. Study drug compliance will be calculated by taking the number of injections (regardless of the actual dose administered) divided by the total number of injections expected to be administered $\times 100$. Insulin glargine compliance will be calculated by taking the total number of injections expected minus the total number of injections missed (regardless of the actual dose administered) divided by the total number of injections expected to be administered $\times 100$. Overall treatment compliance will be summarized descriptively by treatment using the mITT population.

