7.6. Treatment Compliance

Study drug compliance will be determined by the following:

- Study drug administration data will be recorded by the patient and reviewed by the investigator at each study visit.
- The patients will be instructed to return any unused study drug and/or empty cartons at the next visit to the study site for the purpose of performing drug accountability.

In the 3 tirzepatide treatment groups, as well as the placebo group, treatment compliance for each visit interval is defined as taking at least 75% of the required doses of study drug. Patients will be considered to be noncompliant with their insulin glargine treatment if they miss their daily dose of insulin glargine for more than 7 consecutive days or for more than 7 days within a month (that is, a patient is considered to be compliant if they are $\geq 75\%$ compliant with their required

insulin glargine therapy). Similarly, a patient will be considered noncompliant if he or she is judged by the investigator to have intentionally or repeatedly taken more than the prescribed amount of medication.

In addition to the assessment of a patient's compliance with the study drug administration, other aspects of compliance with the study treatments will be assessed at each visit based on the patient's adherence to the visit schedule, completion of study diaries, the results of home BG monitoring, and any other parameters the investigator considers necessary.

Patients considered not to be compliant with their medication and/or the study procedures will receive additional training and instruction, as required, and will be reminded of the importance of complying with the protocol.

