10.3.2.4. Treatment Compliance

Of the patients in the mITT population, frequency counts and percentages of patients prematurely discontinuing study drug, including the reason for premature discontinuation, will be presented by treatment group. A Kaplan-Meier analysis of time from randomization to premature study drug discontinuation by treatment group will be provided.

Treatment compliance is defined as taking at least 75% of required injections of study drug. Frequency counts and percentages of patients compliant to study drug will be summarized by treatment arm using the mITT population.

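### The SAP's only compliance summary accepts study drug or insulin glargine, whereas the protocol defines and promises compliance on study drug alone

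*SAP*

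**What the plan says.** SAP 6.10.1 defines a single combined variable: "Overall treatment compliance will be defined as taking at least 75% of the scheduled study drug or insulin glargine injections". It then gives a percentage formula for each product. Study-drug compliance is injections taken over injections expected. For glargine, "Insulin glargine compliance will be calculated by taking the total number of injections expected minus the total number of injections missed", divided by the number expected. The SAP does not say how the two percentages combine, over what window they are taken, or whether injections are still expected after a patient stops study drug. The only table it commits to is this: "Overall treatment compliance will be summarized descriptively by treatment using the mITT population".

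Protocol 10.3.2.4, the statistical section on the same subject, reads: "Treatment compliance is defined as taking at least 75% of required injections of study drug". It promises frequency counts and percentages of patients compliant with study drug, by arm, in the mITT population. Glargine is not mentioned.

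Protocol 7.6 gives further definitions. For study drug, "treatment compliance for each visit interval is defined as taking at least 75% of the required doses of study drug". For glargine, a patient is noncompliant "if they miss their daily dose of insulin glargine for more than 7 consecutive days or for more than 7 days within a month", and the same sentence equates this with being at least 75% compliant.

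**The concern.** Every arm receives glargine, so a rule that glargine alone can satisfy says little about exposure to the randomized drug. The compliance table is where a reader would look to judge whether a dose effect, or the lack of one, reflects the doses actually taken. Uneven skipping across arms is plausible. Protocol 3.2 reports that gastrointestinal events in the earlier dose-ranging trial were dose-dependent, and Protocol 7.7.1 allows a dose to be omitted for such symptoms. If the table follows the literal wording, a difference between arms in missed study-drug doses could disappear from it.

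SAP 6.2 says that changes from the protocol's analysis methods will be described and justified in the SAP or the study report. SAP 6.10.1 gives no reason for adding glargine to the definition.

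**Working it through.** **Inputs.** The treatment period is 40 weeks (Protocol 5.1). Study drug is weekly, giving 40 expected injections. Glargine is once daily (Protocol 7.1.3), giving 40 × 7 = 280. The threshold is 75% in both documents.

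**Step 1: the protocol's own equivalence.** Compliance in a month is (days − missed) / days.
- 7 missed days: 21/28 = 75.0%, 23/30 = 76.7%, 24/31 = 77.4%.
- 8 missed days: 20/28 = 71.4%, 22/30 = 73.3%, 23/31 = 74.2%.

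The limit of 7 days in a month therefore does match a 75% cut, as Protocol 7.6 says. The SAP's 75% is not in itself looser; only the window can differ.

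**Step 2: a patient who skips alternate doses.** The patient takes 20 weekly doses, at Weeks 0, 2, …, 38, and every glargine dose. Study drug: 20/40 = 50%. Glargine: 280/280 = 100%.

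| Rule | Result |
|---|---|
| SAP, literal *or* | compliant |
| *And* | not compliant |
| Study drug alone (Protocol 10.3.2.4) | not compliant |
| 75% applied to each product in turn | study drug no, glargine yes |

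This patient never discontinues, so all 40 injections are expected whatever convention is chosen for stoppers.

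**Step 3: would another planned output show this patient?**
- Premature discontinuation (SAP 6.10.1): no, the patient has not stopped.
- Duration on study treatment (SAP 6.10): measured from first to last dose plus 7 days, with gaps not subtracted. Here 38 × 7 + 7 = 273 days, against 39 × 7 + 7 = 280 for a full course.
- Re-initiation listing (SAP 6.10.1): requires at least 3 consecutive missed doses and is optional. This patient never misses more than 1 in a row.
- Efficacy analysis set (SAP Table GPGI.6.1): data are cut only after rescue or early discontinuation, so this patient's data stay in.

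**Step 4: the window.** Assume, since the SAP names no window, that the percentages run over the full 40 weeks.
- Glargine: 70 consecutive missed days give (280 − 70)/280 = 75.0%, which passes. Protocol 7.6 calls more than 7 consecutive missed days noncompliant.
- Study drug: missing all 8 doses between the Week 32 and Week 40 visits gives 32/40 = 80% overall, but 0/8 = 0% in that visit interval.

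**Step 5: the denominator after stopping.** A patient who takes one dose and then stops scores 1/40 = 2.5% if all 40 injections remain expected, and 1/1 = 100% if expectation ends at discontinuation. The SAP does not say which applies.

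**The case against.** The strongest reply is that the sentence is loosely worded rather than wrong. Two separate formulas follow it, each with its own denominator, so *or* may mean that the 75% cut is applied to study drug and to glargine in turn. That reading is possible, and on it the 20-of-40 patient is correctly shown as noncompliant with study drug. But the SAP then commits to one overall summary, not two, so the study-drug count promised in the protocol is still not clearly planned.

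A second reply is that poor exposure is visible elsewhere. For patients who stop, this is right. SAP 6.10.1 reports the number stopping early and their reasons, and states: "Time-to-event analysis of premature study treatment discontinuation will be conducted". SAP 6.10 adds duration on treatment, and SAP 6.13.1.4 covers stopping because of adverse events. It does not help for intermittent skipping without discontinuation. The deviation listing in SAP 6.11 might catch some of these patients, but its criteria are in a separate plan.

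Several stronger readings are tempting, and the documents do not support them:
- A reader might infer that a patient who stops study drug in Week 1 is certain to count as compliant. That depends on the literal *or* or on the undefined denominator, and such a patient is reported under discontinuation in any case.
- A reader might pool all 320 injections, so that glargine swamps study drug. The SAP contains no pooled formula.
- A reader might use a patient with no study-drug doses as the example. The mITT population requires at least one.
- A reader might call the protocol's glargine rule tighter than 75%. Protocol 7.6 equates the two, and Step 1 of the check agrees at the monthly scale.
- A reader might say that a percentage without an interval contradicts the protocol throughout. Protocol 10.3.2.4 names no interval either, so on timing the difference is with Protocol 7.6 only.

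**Conclusion.** The point holds as a mismatch in definition. The SAP's one summarized compliance variable includes glargine through *or*, while Protocol 10.3.2.4 specifies study drug alone. Under the literal rule a patient with 50% study-drug compliance is counted as compliant, and the discontinuation, duration and re-initiation outputs would not reveal it. How many patients this would affect cannot be estimated from the documents.

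The consequence is small. The variable feeds one descriptive mITT table. No analysis set in SAP Table GPGI.6.1, no primary or key secondary analysis and no step of the testing strategy uses it, so the efficacy conclusions are not at risk.

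The conclusion assumes the literal reading of *or* and the full schedule of 40 and 280 injections. The figures on the window further assume that the percentages run over all 40 weeks, which is a fair inference from the SAP's wording but is not stated there.

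**What to change.** In SAP 6.10.1:
- Summarize two variables by arm: study-drug compliance, at the 75% threshold of scheduled injections as in Protocol 10.3.2.4, and insulin glargine compliance.
- If an overall figure is kept, replace *or* with *and*.
- State whether expected study-drug injections go on being counted after permanent discontinuation, for example over the full planned 40 weeks. Without this, a one-dose patient could score 100% under any connective.
- State how glargine stops permitted by Protocol 7.4.2 enter the glargine count.
- Reconcile the time window with Protocol 7.6, which uses visit intervals for study drug and consecutive days or a month for glargine.

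The cost is SAP wording and a little more programming. Compliance percentages may come out somewhat lower.
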